Safety and efficacy assessments	
Efficacy assessments:
 
Assessments (CT scan and bone scan) will be performed from the time of enrollment (baseline assessments) and every 12 weeks (\pm 7 working days) from the time of the first administered dose. Radiographic disease progression will be assessed using The Prostate Cancer Clinical Trials Working Group (PCWG2) modified criteria for bone disease and the Response Evaluation Criteria in Solid Tumors (RECIST criteria) version 1.1 for soft-tissue disease. Radiographic disease progression in bone will require persistence of new lesions on a confirmatory bone scan performed at least six weeks later. It is highly recommended to perform additional CT scans and bone scans if clinical progression disease is suspected.
 
During the active phase of the study treatment, each assessment will be performed in accordance with the schedule (Appendix 1: Schedule of study assessments and procedures), regardless of any delay in administration, to prevent bias in the efficacy assessment. If any of the required assessments are not performed, the disease status at that point in time will not be known.
 
Safety assessments:
 
The occurrence and maximum grade of side effects observed throughout the study will be listed and tabulated according to type and dose level. Any adverse events (AEs) that the investigator reports as unrelated to the drug will also be reported. In this study, side effects will be assessed according to the US National Cancer Institute (NCI) Common Terminology Criteria for Adverse Events (CTCAE) version 4.0.
 
Other assessments:
 
To perform the molecular analyses described in this protocol (Appendix 3: Instructions for blood sample collection. Detection of CTCs), patients will be asked to give their consent to the collection of the following biological material:
 
 - Blood samples: These will be collected at the start of the study, at the end of treatment and when documenting disease progression for the purpose of CTC.
Endpoints	
Primary endpoint:
 
The primary endpoint of this study is to assess the efficacy of radium-223 in terms of radiological rPFS.
 
Secondary endpoints:
 
Safety
 
AEs will be evaluated using the NCI-CTCAE version 4.0. Grade 3 or 4 AEs and serious adverse events (SAEs) will be assessed to determine the safety and tolerability of the various combinations of drugs.

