3.2. Study schedule

The design of this study is divided into three well-defined phases:

- **Screening phase**

During this phase, subject eligibility is determined, including the documentation of baseline characteristics. This phase of the study will begin once the informed consent is signed by the patient and the procedures to be performed are described in section 5.1 of the protocol.

- **Treatment phase:**

When a patient is identified and all the study screening criteria have been met, a baseline blood sample will be collected to perform CTCs the patient will be treated with radium-223 at a dose of 55 kBq (after 2015 NIST implementation) per kilogram body weight, given at four-week intervals for six intravenous (IV) injections.

Patients will receive study treatment according to the protocol and will be prematurely discontinued if one of the following situations arises:

- Disease progression is confirmed radiologically and unequivocally. An event for progression will be determined by The Prostate Cancer Clinical Trials Working Group (PCWG2) modified criteria defined as the time from inclusion to the first event in clinical, radiological, or biochemical progression, or death as[21]:

- Bone metastases: The appearance of \geq two new lesions, and, for the first reassessment only, a confirmatory scan performed six or more weeks later that shows a minimum of two or more additional new lesions. The date of progression is the date of the first scan showing the changes.

- Soft-tissue lesions: Assesed according to the Response Evaluation Criteria in Solid Tumors (RECIST criteria) version 1.1.[22].

- Symptoms: Consider independently of other outcome measures. Document pain/analgesia at entry and measure repeatedly at three- to four-week intervals. Ignore early changes (\leq 12 weeks) in pain or health-related quality of life (HRQOL) in the absence of compelling evidence of disease progression. Confirm progression of pain or HRQOL endpoints \geq three weeks later.

- Clinical deterioration: Consider independently of other outcome measures. A deteriorating patient is one who moves from one clinical state to a worse clinical state which increases their individual risk of morbidity, including organ dysfunction, protracted hospital stay, disability, or death.[23].

- AEs which, according to the protocol or in the opinion of the investigator, can cause serious or permanent damage or which rule out further treatment with the study drug.

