A complete physical examination should include an examination of head, eyes, ears, nose, and throat as well as cardiovascular, dermatological, musculoskeletal, respiratory, digestive, genitourinary, and neurological systems. Changes to abnormalities identified during the baseline period should be recorded at all subsequent physical examinations. New or worsening abnormalities should be recorded as AEs, if applicable.

Physical exams should also include, as part of tumor assessment, evaluation of presence and degree of increase of lymph nodes, hepatomegaly, and splenomegaly. Limited physical exams will focus on symptoms.

Response and tumor assessments:

Tumor response will be assessed for all patients, unless they withdraw from the study for any reason not attributable to disease progression confirmed radiologically or clinically and who have not received an acceptable complete assessment of the disease. The non-measurable disease should be documented at screening and be re-assessed at every tumor assessment thereafter.

The initial assessment of tumor response will be performed at the end of cycle three. Subsequently, an efficacy follow-up will be carried out for all patients every 12 weeks ± 7 working days during the study until disease progression, the patient withdraws their consent, or death, whichever comes first. In this study, response and disease progression will be assessed using the PCWG2 guidelines for bone disease and the RECIST criteria version 1.1 for soft-tissue disease. Radiographic disease progression in bone will require persistence of new lesions on a confirmatory bone scan performed at least six weeks later. Soft-tissue progression will not require a confirmatory scan for purposes of analysis (Appendix 2: Response Evaluation Criteria in Solid Tumors Guidelines (RECIST criteria) version 1.1).

A torax, abdomen, and pelvis CT scan or MRI, and a bone scan must be performed at screening (no more than 28 days before the first trial treatment). Tumor assessments should include an assessment of all known and/or suspected sites of the disease wherever possible. Patients should have a series of selected lesions that can be assessed at each tumor assessment. The same radiographic procedure employed at screening should be used throughout the study (e.g., the use of the same contrast protocol for CT scans).

Laboratory assessments:

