 - 4. ECOG performance status will be assessed before trial drug administration and before the administration of each cycle.
 - 5. Relevant concomitant medication will be recorded at screening and on an ongoing basis.
 - 6. FACT-P, Version 04
 - 7. All AEs occurring during the trial and until the treatment discontinuation visit (end of study visit) have to be recorded with grading according to NCI-CTCAE version 4.0.
 - 8. Baseline assessments of the thorax, abdomen, and pelvis (preferably CT or MRI in case of contrast allergy) must be performed no more than 28 days before the first trial treatment. Baseline bone scan must be performed no more than 28 days before the first trial treatment. Post-baseline assessments have to be performed every 12 weeks \pm 7 working days after the first dose using the same imaging method and where possible obtained at the same institution for an individual patient as used during screening until progression disease. Radiographic bone progression will require the persistence of new lesions on a confirmatory scan at least six weeks later. In those patients who receive 6 treatment cycles, the radiological tumour assessment corresponding to week 24 will be performed for the EOT visit.
 - 9. Hematological test will be performed as per local standard of care and clinical indication before treatment administration. These values should be included: hemoglobin, hematocrit, red blood cell count, platelet count, and white blood cell count with differential count (neutrophils, lymphocytes, monocytes, eosinophils, and basophils).
 - 10. Biochemistry test will be performed as per local standard of care and clinical indication before first treatment administration and first day of follow-up. These values should be included: coagulation, chemistry with renal function analysis (serum creatinine, creatinine clearance according to the Cockcroft-Gault formula), liver function (AST, ALT, ALP, direct and total bilirubin), glucose, sodium, potassium, calcium, chloride, magnesium, uric acid, total protein, albumin, and lactate dehydrogenase.
 - 11. Blood sample for central laboratory prior to the start of study treatment, at the end of treatment and at time to documented progression disease (if the patient ends treatment due to progressive disease, only one blood sample will be sent at this point).

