No baseline tumor assessment	Inclusion and Exclusion criteria/ Study procedure	Major	Efficacy	If not baseline values any post-baseline data indicating presence of new bone lesions/visceral lesions could be evaluated as evidence of PD Flag if baseline data (CT and bone scans) are >28 days before day 1 cycle 1.

No post-baseline data indicating presence of ≥ 2 new bone lesions or progression as per RECIST 1.1	Study procedure	Major	Efficacy	No evidence of Radiological PD for patients not discontinued due to increased PSA, symptoms or clinical deterioration.
Visits out of window	Study procedure	Minor	Safety	If not performed every 28 days +7 days until EOT; if not performed every 3 months after EOT or if EOS not performed within 3 months after progression, lost to FUP.
Local laboratory tests out of window	Study procedure	Major	Safety	If tests scheduled for day 1 of all cycles (including screening) not performed within 72 hours prior to the dose
Screening assessments out of window	Study procedure	Case by case	Safety	If done >28 days before day 1 cycle 1. Not applicable to local lab tests.
Assessments not done during treatment period (lab value, HRQoL..)	Study procedure	Case by case	Safety	Not applicable to Radiological Assessments. Flag if systematically not done.
Blood sample for translational study not obtained or obtained at incorrect timepoint	Study procedure	Case by case	Efficacy	Depending on which sample is not collected.
Blood sample for translational study obtained out of window at screening	Study procedure	Case by case	Efficacy	Sample not obtained within 72 hours prior to the first dose
Adequate follow-up	Study procedure	Major	Efficacy	If no post-treatment evaluation according to protocol
Prohibited medication was taken	Concomitant medication	Major	Efficacy	If any therapies intended for the treatment of cancer prior to EoT (Cytotoxic chemotherapy, other systemic radioisotopes,

EudraCT number: 2016-001888-36

				radiotherapy, abiraterone acetate, enzalutamide or any antiandrogen)
Prohibited medication was taken	Concomitant medication	On a case by case	Efficacy Safety	If another investigational drug prior to EoT
Subject not withdrawn as per protocol	Administrative and Other	Major	GCP	If data is obtained after withdrawal

\* Major protocol deviation excludes from the full analysis set

\*\* Identification of clinically relevant conditions from the Medical History

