#### 7.1.1 *Primary analysis*

The primary efficacy endpoint is the median PFS achieved with radium-223 treatment. The PFS will be evaluated at the first 34 months period of the study. The PFS will not be evaluated at the 2-years extension of the study for safety.

PFS is a composite endpoint defined as the time from the start of the radium-223 treatment to disease progression in bone or soft-tissue, symptoms, or death, according to the modified PCWG2 criteria.

Objective radiographic disease progression is defined as the presence of at least one of the following conditions:

- Bone lesion progression (appearance of  $\geq$  two new bone lesions compared to baseline).
- Soft-tissue lesion progression according to the RECIST criteria version 1.1.
- Presence of symptomatic skeletal events (pathological fractures, spinal cord compression, radiation or surgery to bone), which should have been reported as adverse event/serious adverse events.

Patients with no progression will be censored at the date of their last evaluation (see Table 1 – Appendix I).

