**Appendix I**

Table 1. Censoring rules for PFS

Situation	Date of progression or censoring	Outcome
Progression documented between scheduled visits	
Earliest of:
 

• Date of radiological assessment showing new lesion (if progression is based on new lesion); or

• Date of last radiological assessment of measured lesions (if progression is based on increase in sum of measured lesions); or

• Bone lesion progression (appearance of <math>\geq</math> two new bone lesions compared to baseline); or

• Presence of symptomatic skeletal events (pathological fractures, spinal cord compression, radiation or surgery to bone)

	Progressed
Death before first progression disease assessment	Date of death	Progressed
Death between adequate assessment visits	Date of death	Progressed
No progression	Date of last radiological assessment of measured lesions	Censored
Treatment discontinuation for undocumented progression	Date of last radiological assessment of measured lesions	Censored
Treatment discontinuation for toxicity or other reason	Date of last radiological assessment of measured lesions	Censored
Death or progression after more than one missed visit	Date of last radiological assessment of measured lesions	Censored

EudraCT number: 2016-001888-36

Table 2. Censoring rules for OS

Situation	End date	Status
Death during study follow-up	Date of death	Death
The patient is alive at last follow-up	Date of last follow-up	Censored

EudraCT number: 2016-001888-36

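### The primary-endpoint definition omits the six-week persistence rule for bone progression stated elsewhere in the protocol, and Protocol 3.2 gives a third, incompatible bone rule.

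*SAP*

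**What the plan says.** Three rules for progression in bone appear.

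- **Rule A, the analysis text.** Protocol 8.3.1 with Table 2, and SAP 7.1.1 with Appendix I Table 1, count an event at two or more "two new bone lesions compared to baseline". Confirmation is neither required nor excluded. Both sections place the composite endpoint under the modified PCWG2 criteria.
- **Rule B, the assessment text.** The protocol synopsis and Protocol 5.2 say: "Radiographic disease progression in bone will require persistence of new lesions on a confirmatory bone scan performed at least six weeks later". Appendix 1 note 8 agrees: "Radiographic bone progression will require the persistence of new lesions on a confirmatory scan at least six weeks later". Section 5.2 then adds: "Soft-tissue progression will not require a confirmatory scan for purposes of analysis".
- **Rule C, Protocol 3.2.** At the first reassessment only, a scan six or more weeks later must show at least two additional new lesions. Progression is dated at the first scan that showed the change.

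The PCWG2 label is attached to more than one rule. The synopsis says "Radiographic disease progression will be assessed using The Prostate Cancer Clinical Trials Working Group (PCWG2) modified criteria for bone disease" and goes on to rule B. Protocol 3.2 says "An event for progression will be determined by The Prostate Cancer Clinical Trials Working Group (PCWG2) modified criteria" and goes on to rule C.

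Protocol 8.3.5 and SAP 7.1 state that evaluations are made at the sites, without central review.

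**The concern.** The definition that a programmer will code is the one in SAP 7.1.1 and Appendix I. Coded as it stands, two new lesions at week 12 that are absent six weeks later are a primary-endpoint event. Under Protocol 5.2 they are not. Someone who tries to supply the missing confirmation rule through the PCWG2 reference finds two candidates that disagree.

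The median PFS of a single-arm, open-label trial with site-read scans is at stake. Without one written rule, the choice could be made after the data have been seen, and the reported median depends on it.

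**Working it through.** **1. The rules applied to the same patient.** Take two new bone lesions at the week-12 scan (the first reassessment). Read rule B with the two-lesion threshold of rule A, since rule B names no number.

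| Scan six or more weeks later | Rule A | Rule B | Rule C |
|---|---|---|---|
| Lesions gone | event | no event | no event |
| Lesions persist, none added | event | event | no event |
| Lesions persist, two more added | event | event | event |

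After the first reassessment, rule C asks for no confirmation while rule B still does. The three are therefore different rules, not paraphrases.

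**2. The plan's sample size does not choose between them.** Inputs from Protocol 8.2: null median 3 months, target 6.3 months, one-sided alpha 0.05, power 80%, accrual 23 months plus 11 months of follow-up, 25% AR-V7-positive.

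- Events = (1.645 + 0.842)² / [ln(3/6.3)]² = 6.183 / 0.5505 = 11.23.
- Probability of an event under the target = 0.892, so n = 11.23 / 0.892 = 12.6, rounded up to 13.
- Total = 13 / 0.25 = 52.

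The stated 52 is reproduced. It depends on the two medians only and is silent on how a bone event is confirmed.

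**3. Size of the effect (illustration).** The documents give no rate of transient lesions. Assume that a fraction r of patients event-free at week 12 show non-persisting lesions, which rule A counts and rule B does not. Scans are every 84 days (84 / 30.4375 = 2.76 months), and every event is dated at a scan.

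- At a true median of 6.3 months, the proportion event-free per interval is 2^(−2.76/6.3) = 0.738.
- Expected week-12 events = 52 × (0.262 + 0.738 r): 13.6 at r = 0, 17.46 at r = 0.10 and 21.3 at r = 0.20.

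I simulated 20,000 trials per setting with n = 52, the planned accrual and follow-up, and the SAP's exponential maximum-likelihood test of a 3-month median at one-sided 0.05:

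| r | Week-12 events of 52 | Fitted median (months) | Chance of a positive trial |
|---|---|---|---|
| 0 | 13.6 | 7.3 | 1.00 |
| 0.10 | 17.4 | 6.7 | 1.00 |
| 0.20 | 21.3 | 6.1 | 1.00 |

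The fitted median exceeds 6.3 at r = 0 because progression is recorded at the next scan.

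**4. Lower true medians.** Median = 2.76 × ln 0.5 / ln p, where p is the proportion event-free per scan interval. The last three columns give the chance of a positive trial.

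| p | True median (months) | r = 0 | r = 0.10 | r = 0.20 |
|---|---|---|---|---|
| 0.65 | 4.4 | 1.00 | 0.99 | 0.96 |
| 0.60 | 3.7 | 0.98 | 0.93 | 0.81 |
| 0.55 | 3.2 | 0.87 | 0.70 | 0.48 |
| 0.50 | 2.8 | 0.54 | 0.34 | 0.17 |

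The first three rows are power. The last lies below the 3-month null, so its entries are false-positive rates; there, requiring persistence (moving from r = 0.10 to r = 0) raises the rate from 0.34 to 0.54.

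The near-null levels are inflated by dating every event at a scan. At a true 3-month median the chance is about 0.75 if all events are scan-dated, 0.50 if a quarter carry exact dates (as deaths and skeletal events would) and 0.26 if half do. Only the differences across r bear on this point.

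**The case against.** **The gap between A and B is an omission, not a conflict.** The analysis sections invoke PCWG2, and section 5.2 exempts only soft tissue from confirmation when it speaks of analysis, so the short list in 8.3.1 may be shorthand for rule B. This is a fair reading, and probably the intended one. It does not close the gap: rule C carries the same label, cannot be squared with rule B, and the SAP never states confirmation.

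**Protocol 3.2 concerns stopping treatment.** It does sit in the list of reasons for discontinuation, although it is worded as the definition of a progression event. A reader might infer that its start point (inclusion) and its clinical and biochemical events create a rival primary endpoint. The documents do not support that. Protocol 8.3.1, SAP 7.1.1 and SAP 7.5 all start at first dose, and none of the analysis event lists contains PSA progression. Those differences are editorial.

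**The decision is not in danger.** At the planned median this stands: the trial is positive under either rule at every assumed rate. What moves is the reported median.

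**Confirmatory scans may be missing.** This also stands. Note 8 requires them, but the Appendix 1 table has no visit for them and scheduled imaging ends at progression. It cannot be taken for granted that the data exist.

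**Conclusion.** The point holds and should be fixed before analysis. The event definition as listed leaves out a rule that the protocol states three times, and Protocol 3.2 contradicts that rule.

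A reader might infer that leaving out confirmation flatters the drug. It does the opposite: extra early events shorten PFS. Under the assumed 0 to 20% of transient lesions and scan-dated events, the fitted median at the planned effect ranges from about 7.3 to 6.1 months and the chance of success does not change. The positive or negative conclusion becomes sensitive only for true medians near 3 months.

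A reader might also attach to this point the censoring of patients who stop treatment for undocumented progression. Both censoring tables prespecify that rule explicitly, so it is no part of this ambiguity.

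The textual finding rests on no assumption. The sizes are illustrative and rest on the assumed rates and on events dated at 12-weekly scans.

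**What to change.** Before analysis:

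1. Write the protocol's own persistence rule (synopsis, 5.2, Appendix 1 note 8) into Protocol 8.3.1 and Table 2, and into SAP 7.1.1 and Appendix I: two or more new bone lesions versus baseline that persist on a scan at least six weeks later.
2. Date the event at the first scan showing the new lesions. Protocol 3.2 already does so, and the tables' progression row ("Date of radiological assessment showing new lesion") fits.
3. State how a missing confirmatory scan is handled, for example as an event at the first scan, which does not favour the drug. If many are missing, this moves the analysis back towards rule A, so report their number.
4. Add one sensitivity analysis counting unconfirmed bone progression as an event.
5. Reconcile Protocol 3.2 with these passages. This is for the sponsor; no rule for stopping treatment is proposed here.

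Editorial only: use one name for the endpoint (radiological PFS or composite PFS), align the word symptoms in the PFS sentence with the symptomatic skeletal events actually listed, and align the start point and biochemical wording of 3.2 with 8.3.1 and SAP 7.1.1 and 7.5.

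The cost is wording plus one extra analysis. The confirmatory scans are already required, but the sponsor should check that they are being done and captured, because the schedule shows no visit for them.

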Definition of hospitalization: AEs that require hospitalization are considered serious. In general, hospitalization is considered as such when the patient has stayed (usually overnight) at a hospital or emergency room for observation or treatment that could not have been performed in a doctor's office or outpatient site. If there is some doubt as to whether the hospital stay can be considered "hospitalization" or whether it was necessary or not, the AE should be considered serious.

Hospitalization for scheduled surgery or standard clinical procedures which are not the result of an AE will not be considered an AE. If an incident arises during the procedure that is considered harmful, this should be reported as an AE and should be designated "serious" or "not serious" as per the standard criteria.

Definition of an event that is clinically or medically significant: Significant medical events that do not have a fatal outcome, regardless of whether they are life-threatening or require hospitalization, may be considered SAEs when, according to the appropriate medical opinion they put the patient's life at risk and may require medical or surgical intervention to prevent any of the outcomes listed in this definition. Examples of such medical events include allergic bronchospasm which requires intensive treatment in an emergency room or at home; blood dyscrasias; convulsions that do not result in hospitalization; or development of drug dependency or drug abuse. Clinically/medically significant events must be reported as SAEs.

For this clinical study and, according to this protocol, SAEs and hospitalizations related solely and unequivocally to the progression of the established tumor disease will not be treated as SAEs with regards to reporting obligations.

If the investigator becomes aware of a SAE at any time after the end of administration of study treatment and believes that it is possibly related to the study treatment (serious adverse reactions), he/she should notify the Sponsor.

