### 7.2.1 Summary statistics

#### Efficacy:

- OS is defined as the time from inclusion until death from any cause or the last date the patient was known to be alive. Patients who are lost to follow-up and the patients who are alive at the date of data cut-off are censored at the date the patient was last known alive (censoring rules are specified in
  - Appendix I). The OS will be assessed by cohorts.
- Time to first SSE is defined as the time from treatment initiation until SSE (pathological fractures, vertebral or non-vertebral, spinal cord compression, radiation or surgery to bone). For all other events, the start date of the event/medication/therapy was used as the time of the event. If an event has not occurred at the time of the analysis or the patient has been lost to follow-up, the time-to-event variables will be censored at the last disease assessment date.
- The time from the first study drug administration to when PSA progression was observed, defined as:
  - 1) In subjects with no PSA decline from baseline:  
a greater than or equal to 25% increase from baseline value and an increase in absolute value of greater than or equal to 2 ng/mL, at least 12 weeks from baseline;
  - 2) In subjects with initial PSA decline from baseline:

the time from start of treatment to first PSA increase that is greater than or equal to 25% increase and at least 2 ng/mL above the nadir value, which was confirmed by a second value obtained three or more weeks later.

- Determination percentage of PSA progression (defined as PSA elevation  $\geq 25\%$  and  $\geq 2$  ng/mL after 12 weeks).
- Alkaline phosphatase (AF) level response, normalization of alkaline phosphatase level (progression defined as AF elevation  $\geq 25\%$  after 12 weeks). The patients will be classified according on whether there is AF progression or not.
- Radiographic progression-free survival (rPFS) depending on AR-V7 status.

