#### **8.4.2 *Concomitant Medications***

The number and percent of unique patients taking concomitant medications will be summarized by ATC code. Elective surgeries/procedures performed during the study will be presented in a listing.

The following are conventions that will be used to classify individual medications as prior and/or concomitant:

- Medications with stop dates prior to enrollment will be considered prior.
- Medications with missing stop dates or stop dates the day of or after enrollment will be considered concomitant, regardless of start date. Additionally, if the start date is prior to enrollment or missing, the medication will also be considered prior.

Frequencies and by-subject listing of all prior and concomitant medications will be provided, containing variables listed on Prior/Concomitant Assessment eCRF, their corresponding categories (Prior or Concomitant), and WHO Anatomical Therapeutic Chemical (ATC) level 4.

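### Radiation to bone is a primary PFS event, yet radiotherapy before end of treatment is a Major deviation with no exception, so a patient can be excluded because of his own outcome

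*SAP*

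**What the plan says.** **The event.** SAP 7.1.1 lists skeletal events among the conditions for progression, with radiation and surgery to bone among them, and adds "which should have been reported as adverse event/serious adverse events". The PFS censoring table in SAP Appendix I scores "Presence of symptomatic skeletal events (pathological fractures, spinal cord compression, radiation or surgery to bone" as progressed and sets no reporting condition. Protocol 8.3.1 and its Table 2 do the same.

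**The deviation.** The deviation table in SAP 6.1 has a prohibited-medication row graded Major. Its comment reads "If any therapies intended for the treatment of cancer prior to EoT" and goes on to list radiotherapy by name, without regard to site or purpose. Another Major row covers patients with neither two or more new bone lesions nor RECIST progression, unless they stopped for rising PSA, symptoms or clinical deterioration.

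**The consequence.** The text of SAP 6.1 says that a Major deviation removes a patient from the per protocol set. The footnote to the table says that it removes him from the full analysis set. The full analysis set in SAP 6 requires only that the selection criteria are met and one dose is received. SAP 7.1.1 makes the full analysis set primary and the per protocol set supportive.

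**The concern.** The same act is both an endpoint and a ground for exclusion. A patient who receives radiotherapy to a bone metastasis before end of treatment has, by SAP 7.1.1, reached his primary event. By SAP 6.1 he is then taken out of an analysis set because of it. The exclusion is not independent of outcome: it selects early failures, and the patients who remain look better than the population treated. In a single-arm trial tested against a fixed 3-month null there is no control group in which the same selection could offset it.

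Under the text of 6.1 the damage is confined to the supportive analysis. Under the footnote it reaches the primary one. The SAP does not say which governs.

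**Working it through.** **1. Inputs.** N = 52; one-sided alpha 0.05; 80% power; median PFS 3 against 6.3 months; 23 months of accrual plus 11 of follow-up; AR-V7-positive share 25% (Protocol 8.2). The primary test is the exponential maximum-likelihood test (SAP 7.1.1).

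**2. The plan's own figure.**
- Events needed: (1.645 + 0.842)² / [ln(6.3/3)]² = 11.23.
- Event probability at 6.3 months, with λ = ln 2/6.3 = 0.110: 1 − (e^(−11λ) − e^(−34λ))/(23λ) = 0.892.
- N = 11.23/0.892 = 12.6, so 13, and 13/0.25 = 52. Power at 13 is 81.1%.

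The stated 13 and 52 reproduce, so the same test is used below.

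**3. How many patients the exclusion reaches.** Let f be the share of PFS events that are skeletal and would trigger exclusion. The documents give no value; 5%, 10% and 20% are assumed. End of treatment is put at 24 weeks because Protocol Appendix 1, footnote 8, assigns the week-24 scan to the end-of-treatment visit. That is E = 24 × 7/30.44 = 5.52 months. At a true median of 3.0 months, λ = ln 2/3 = 0.231 and the chance of an event before E is 1 − e^(−λE) = 0.721. Patients left: 52 × (1 − 0.721f) = 50.1, 48.3, 44.5.

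**4. Direction and size of the bias.** Ignoring administrative censoring (about 1.5% of patients at this median), the mean time among those kept is

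[1/λ − f × ((1 − e^(−λE))/λ − E e^(−λE))] / [1 − f(1 − e^(−λE))] = (4.328 − 1.577f)/(1 − 0.721f).

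Multiplied by ln 2, this gives apparent medians of 3.06, 3.12 and 3.25 months, which are 1.8%, 3.8% and 8.3% too high.

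**5. Simulation with the accrual pattern and the exponential test** (20,000 trials per scenario; true median 3.0 months; skeletal events before 24 weeks removed):

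| Assumed share f | Mean n | Median estimate (months) | Rejection, one-sided 0.05 |
|---|---|---|---|
| 0 | 52.0 | 2.98 | 3.9% |
| 5% | 50.1 | 3.04 | 5.1% |
| 10% | 48.3 | 3.09 | 6.7% |
| 20% | 44.5 | 3.23 | 11.0% |

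Relative to 2.98, the shifts match step 4. At a true 6.3 months, the median estimate moves from 6.27 to 6.39, 6.52 and 6.78, and rejection stays above 99% throughout.

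**6. Where the bias comes from.** If patients with a skeletal first event are removed whenever it occurs, rejection at 3.0 months is 4.2%, 4.3% and 5.0%, hardly above the 4% baseline. It is the cut at end of treatment, which removes early events and keeps late ones, that inflates the error. The second Major row has no such time limit. It also reaches patients with no event at all, whose removal would pull the other way; that effect is not counted here.

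**The case against.** **Against the exclusion.** The radiotherapy row does not name surgery; a bone-surgery patient can be reached only through the no-radiological-progression row, and that row spares those who stopped for symptoms. One could argue that palliative radiotherapy is not therapy for the cancer, but the row names radiotherapy without qualification. If end of treatment means the last injection, which is where Protocol 3.5 ends the treatment period, radiotherapy that itself ends treatment would fall after it. This reading is open, but the SAP does not adopt it, and the schedule places the end-of-treatment visit at week 24, after the sixth injection. SAP 6.1 also has deviations reviewed before database lock, so the team might waive the rule. That is discretion exercised after outcomes are known in an open-label trial, which the SAP should not need. What stands is that the primary analysis is exposed only if the footnote governs.

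**A stronger reading.** A reader might infer that the AE/SAE phrase in SAP 7.1.1 makes skeletal events drop out of PFS. The documents do not support that.
- The phrase says where the events are expected to appear; neither document's censoring table makes it a condition.
- Protocol 7.1 says "Hospitalization for scheduled surgery or standard clinical procedures which are not the result of an AE will not be considered an AE", and the qualifier matters: surgery for a fracture or cord compression ordinarily does result from an AE.
- The sentence "SAEs and hospitalizations related solely and unequivocally to the progression of the established tumor disease will not be treated as SAEs" is limited to reporting obligations. Protocol 7.2 still requires all AEs on the CRF, and SAP 7.1.1 accepts AEs as well as SAEs.
- Protocol Appendix 1 has AE and concomitant-medication reporting from screening through progression. SAP 8.4.2 adds that "Elective surgeries/procedures performed during the study will be presented in a listing".
- For time to first SSE, "the start date of the event/medication/therapy was used as the time of the event" fixes a date, not a data source, so it does not establish a conflict with the primary endpoint.

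Total non-capture, with patients censored at their last scan, would give rejection of 7%, 11% and 26% at shares of 5%, 10% and 20%. Nothing in the documents indicates total non-capture, so these figures do not size the point.

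**Conclusion.** The SAP is wrong as written on exclusion. Its rule removes a patient for an event that its endpoint definition counts, and its footnote contradicts its own set definitions. In whichever set is affected, the false-positive rate at a true 3.0 months rises from about 4% to about 5%, 7% or 11% for assumed shares of 5%, 10% or 20%, and the median estimate rises by about 0.06 to 0.25 months (3.04 − 2.98 to 3.23 − 2.98). The harm is upward bias and type I error, not lost power.

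The size rests on exponential PFS, a skeletal share that does not vary with time, end of treatment at 24 weeks, and every such early event being excluded. Fewer exclusions mean a smaller effect. The AE/SAE wording is a risk of missed events that deserves a clarifying sentence, not a demonstrated loss.

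**What to change.** 1. **SAP 6.1, deviation table.** State that radiotherapy or surgery to bone meeting the skeletal-event definition is a PFS event and does not by itself exclude the patient from the full analysis or per protocol set, under either the prohibited-medication row or the no-radiological-progression row. It can still be recorded as a deviation.
2. **SAP 6.1, footnote.** Reconcile it with the full analysis set definition in SAP 6 and with the text of 6.1, so that one statement says which set a Major deviation affects. Define end of treatment for this row.
3. **SAP 7.1.1, clarification.** State that a skeletal event counts whether or not it was filed as an AE or SAE, that it is derived from the AE, concomitant-therapy and procedure records together, and that it is dated as for time to first SSE.

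The cost is SAP wording, one derivation program and a few site queries. No new data collection is needed, and the rules on permitted treatment are untouched.
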